It is the responsibility of the DSMC clinician to review all reported events, evaluate the events as they are reported; and communicate a response to the Investigator, event reporter and the members of DSMC. The review will include but not be limited to the information reported; there may be times when additional information is needed in order for an assessment to be made and further communication directly with the investigator may be warranted. DSMC reserves the right to disagree with the Investigator's assessment. If DSMC does not agree with the Investigator, DSMC reserves the right to suspend the trial pending further investigation. If there is any immediate danger or harm that could be present for a future patient based on the information provided in the DSMC report then an immediate suspension of enrollment should be considered.

AMENDMENTS TO PREVIOUS REPORTS

If all pertinent information is unavailable with the initial submission, once the additional information is available **do not submit a new report**. Rather, go to the original email that was sent to the DSMC and using that email "reply to all". Entitle this new email "**Amendment** for (list date of event and patient ID)" this will avoid duplications of the same event. List the additional information being reported. This information needs to be entered into WISER as well. To do this, go to the Subject console and click SAEs on the left

A Prospective Randomized Phase II Study of 1 vs 2 Fractions of
 Palliative Radiation Therapy for Patients with Symptomatic Bone Metastasis
 Comprehensive Cancer Center of Wake Forest University (CCCFWU)
 CCCFWU # 01416

column. Click on the appropriate SAE number that needs updating. Then click Update. This will allow additional information to be added.

Acronyms

AE – Adverse Event

DSMC-Data and Safety Monitoring Committee

SAE-Serious Adverse Event

WFBCCC – Wake Forest Baptist Comprehensive Cancer Center

NCI-National Cancer Institute

WISER –Wake Integrated Solution for Enterprise Research

Screen Shots:

The following screen shots come from the SAE Console within the Subject Console in WISER.

Screen Shot 1:

Screen Shot 2:

Screen Shot 3:

Subject Console

Protocol No: CCCWFU00215
MRI: _____

Subject SAE Update

Event Date: 10/22/2015 Event End Date: _____ Event Occurred: _____ Reported Date: 10/23/2015 Reported By: _____

Protocol Status: OPEN TO ACCRUAL Subject Name: _____ Subject Status: ON TREATMENT Sequence No: _____

Appendix E – Baseline Data Collection Form**1. Medical history (check all that apply):**

Myocardial infarction
 Congestive heart failure
 Peripheral vascular disease
 Cerebrovascular disease
 Dementia
 Chronic pulmonary disease
 Connective tissue disease
 Peptic ulcer disease
 Liver disease – mild moderate severe
 Diabetes – end organ damage? Yes No
 Hemiplegia
 Other cancer – specify _____
 AIDS
 Other medical condition – specify _____

Other sites of metastases: Yes No N/A **If yes:**

a. Brain: Yes No
b. Liver: Yes No
c. Other: _____

2. Medications (including pain meds):

Concurrent medications:

a. Name: _____ Dose: _____ Frequency: _____ Date started: _____
b. Name: _____ Dose: _____ Frequency: _____ Date started: _____
c. Name: _____ Dose: _____ Frequency: _____ Date started: _____
d. Name: _____ Dose: _____ Frequency: _____ Date started: _____
e. Name: _____ Dose: _____ Frequency: _____ Date started: _____
f. Name: _____ Dose: _____ Frequency: _____ Date started: _____

Currently using bisphosphonates/Denosumab? Yes No **If yes:**

Name: _____ Dose: _____ Frequency: _____ Started: _____ Prior Cancer Therapy:
a. Name: _____ Treatment Regimen: _____
b. Name: _____ Treatment Regimen: _____
c. Name: _____ Treatment Regimen: _____

Change in systemic chemotherapy in past 4 weeks? Yes No N/A Change in hormonal therapy in past 4 weeks? Yes No N/A Change in use of bisphosphonates in past 4 weeks? Yes No N/A Change in immunotherapy in past 4 weeks? Yes No N/A **3. Performance Status (check one):**

ECOG PERFORMANCE STATUS	
GRADE	Description
 0	Fully active, able to carry on all pre-disease performance without restriction
 1	Restricted in physically strenuous activity but ambulatory and able to carry out work of a light or sedentary nature, e.g., light house work, office work
 2	Ambulatory and capable of all self-care, but unable to carry out any work activities. Up and about more than 50% of waking hours
 3	Capable of only limited self-care, confined to bed or chair more than 50% of waking hours
 4	Completely disabled. Cannot carry on any self-care. Totally confined to bed or chair
 5	Dead

4. Nutrition status:

- a. Height: _____
- b. Weight: _____
- c. BMI (kg/M²) _____
- d. History of weight loss: (within the last three months prior to enrollment) Yes No
If yes, date of weight loss: ___/___/
If yes, amount of weight loss: _____

5. Vital signs:

- a. HR _____
- b. BP ___ / ___
- c. RR _____
- d. Temp (°F) _____

6. Physical Exam

Derm –	 WNL	 Abnormal, specify _____
HEENT –	 WNL	 Abnormal, specify _____
CV –	 WNL	 Abnormal, specify _____
Pulm –	 WNL	 Abnormal, specify _____
GI –	 WNL	 Abnormal, specify _____
Other –	 Abnormal, specify _____	

7. Documentation of negative pregnancy test for women of child-bearing potential?

Yes No , reason _____ Not applicable

Appendix F – Treatment Data Collection Form

Time point of assessment:

Treatment administration Tx #1 Tx #2
 3 months post treatment
 6 months post treatment

1. Nutrition status:

a. Weight: _____
b. BMI (kg/M²) _____
c. History of weight loss: (since last assessment) Yes No
If yes, date of weight loss: ___ / ___ / ___
If yes, amount of weight loss: _____

2. Vital signs:

a. HR _____
b. BP ___ / ___
c. RR _____
d. Temp (°F) _____

Appendix G – Patient QuestionnaireTime point of assessment:

Baseline
 3 months post treatment
 6 months post treatment

	Not at All	A Little	Quite a Bit	Very Much
1. Do you have any trouble taking a short walk outside of the house?	1	2	3	4
2. Do you need to stay in bed or a chair during the day?	1	2	3	4
3. Do you need help with eating, dressing, washing yourself or using the toilet?	1	2	3	4

During the past week:	Not at All	A Little	Quite a Bit	Very Much
4. Were you short of breath?	1	2	3	4
5. Have you had pain?	1	2	3	4
6. Have you had trouble sleeping?	1	2	3	4
7. Have you felt weak?	1	2	3	4
8. Have you lacked appetite?	1	2	3	4
9. Have you felt nauseated?	1	2	3	4

During the past week:

	Not at All	A Little	Quite a Bit	Very Much
--	------------	----------	-------------	-----------

10. Have you been constipated?	1	2	3	4
11. Were you tired?	1	2	3	4
12. Did pain interfere with your daily activities?	1	2	3	4
13. Did you feel tense?	1	2	3	4
14. Did you feel depressed?	1	2	3	4

For the following question please circle the number between 1 and 7 that best applies to you15. How would you rate your overall quality of life during the past week?

1 2 3 4 5 6 7

Very poor

Excellent

We are interested in knowing about the stresses you are experiencing with your treatment. Please answer each question regarding how you have perceived stress in the past week on a scale from 1 = "Never" to 5 = "Very Often".

	Never	Almost Never	Sometimes	Fairly Often	Very Often
In the last month, how often have you been upset because of something that happened unexpectedly?	1	2	3	4	5
In the last month, how often have you felt that you were unable to control the important things in your life?	1	2	3	4	5
In the last month, how often have you felt nervous and "stressed"?	1	2	3	4	5
In the last month, how often have you felt confident about your ability to handle your personal problems?	1	2	3	4	5
In the last month, how often have you felt that things were going your way?	1	2	3	4	5
In the last month, how often have you found that you could not cope with all the things that you had to do?	1	2	3	4	5
In the last month, how often have you been able to control irritations in your life?	1	2	3	4	5
In the last month, how often have you felt that you were on top of things?	1	2	3	4	5
In the last month, how often have you been angered because of things that were outside your control?	1	2	3	4	5

I felt I had enough time with my doctor.	1	2	3	4	5
My questions were answered to my satisfaction.	1	2	3	4	5
Making an appointment was easy.	1	2	3	4	5
I knew what the next step in my care would be.	1	2	3	4	5
I feel confident in how I deal with the health care system.	1	2	3	4	5
I was able to get the advice I needed about my health issues.	1	2	3	4	5
I knew who to contact when I had a question.	1	2	3	4	5
I received all the services I needed.	1	2	3	4	5
I am satisfied with the care I received.	1	2	3	4	5
The doctors seemed to communicate well about my care.	1	2	3	4	5
I received high quality care from my regular doctor.	1	2	3	4	5
I received high quality care from my specialists.	1	2	3	4	5
My regular doctor was informed about the results of the tests I got.	1	2	3	4	5

Appendix H – Numerical Rating Pain Scale (NRPS)

Time point of assessment:

- Screening/Baseline
- 1-month post treatment
- 2-months post treatment
- 3 months post treatment
- 6 months post treatment

Please rate your pain by circling the one number that best describes your pain at its WORST in the past 3 days.

Site of Pain: _____

Toxicity Evaluation:

Did the patient report any adverse events or toxicities? **Y** / **N** / **N/A**

If Yes, Describe and add to AE Log:

Any changes to the patient's medications? **Y** / **N** / **N/A**

If yes, Name: _____ Dose: _____ Frequency: _____ Date started: _____

Name: Dose: Frequency: Date started:

Name: Dose: Frequency: Date started:

Name: Dose: Frequency: Date started:

Appendix I – CCCWFU 01416 Adverse Event (AE) Log

PI: _____	PID: _____	MRN: _____									
Start Date: _____	End Date: _____	Time Point (choose one)	1 month								
Adverse Event CTC Term	Value (-5 if nonnumeric)	Grade (0-5) per CTC	Start Date	Attribution 1=Related 2=Probably 3=Possible 4=Unlikely 5=Unrelated	Treating MD Initials/Date	End Date	Expected 1=Yes 0=No	Serious Adverse Event (SAE) 1=Yes 0=No	Dose Limiting Toxicity (DLT) 1=Yes 0=No	Action Taken 1=None 2=Tx withheld 3=Tx D/C 4=Tx adjusted 5=Other	Reportable? (1-IRB 2-STRC, 3-FDA 4-Sponsor)
Nausea							1				
Vomiting							1				
Diarrhea							1				
Skin erythema							1				
alopecia							1				
esophagitis							1				
myelosuppression							1				
Urinary urgency							1				
Urinary frequency							1				
pneumonitis							1				
Pain (increased from baseline)											

Serious Adverse Event: Hospitalization; Disability; Birth Defect; Life-threatening; Death.

CTCAE Version 4 - http://evs.nci.nih.gov/ftp1/CTCAE/CTCAE_4.03_2010-06-14_QuickReference_8.5x11.pdf

CCCWU # 01416

Patient ID: _____ Date of completion: _____

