8.0 Adverse Events List and Reporting Requirements

8.1 Adverse Event List for Radiation Treatment

Expected side effects, depending on the area treated, include nausea, vomiting, diarrhea, skin erythema and alopecia in the irradiated area, esophagitis, myelosuppression, urinary urgency and frequency, and pneumonitis.

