8.2 Adverse Event Characteristics

- **CTCAE term (AE description) and grade:** The descriptions and grading scales found in the revised NCI Common Terminology Criteria for Adverse Events (CTCAE) version 4.0 will be utilized for AE reporting. All appropriate treatment areas should have access to a copy of the CTCAE version 4.0. A copy of the CTCAE version 4.0 can be downloaded from the CTEP web site (<http://ctep.cancer.gov>).
- **‘Expectedness’:** AEs can be ‘Unexpected’ or ‘Expected’ (see Section 7.1 above) for expedited reporting purposes only.
- **Attribution** of the AE:
 - Definite – The AE is **clearly related** to the study treatment.
 - Probable – The AE is **likely related** to the study treatment.
 - Possible – The AE **may be related** to the study treatment.
 - Unlikely – The AE is **doubtfully related** to the study treatment.
 - Unrelated – The AE is **clearly NOT related** to the study treatment.

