8.3 DSMC SAE Reporting Requirements

The Data Safety Monitoring Committee (DSMC) is responsible for reviewing SAEs for WFBCCC Institutional studies as outlined in Appendix D. All Adverse Events that occur during protocol intervention and are coded as either 1) unexpected grade 4, 2) unplanned inpatient hospitalization \geq 24 hours (regardless of grade), or grade 5 (death) must be reported to the DSMC using the SAE console in WISER.

All WFBCCC Clinical Protocol and Data Management (CPDM) staff members assisting a Principal Investigator in investigating, documenting and reporting an SAE qualifying for DSMC reporting are responsible for informing a clinical member of the DSMC as well as the entire committee via the email notification procedure of the occurrence of an SAE.

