All Adverse Events (AEs) and Serious Adverse Events (SAEs) that occur on any patients enrolled on WFBCCC Investigator Initiated Interventional trials must be entered into the WISER system. The only exception to this requirement is for patients enrolled on NCORP trials at non- WFBCCC sites. AEs and SAEs for NCORP patients enrolled at WFBCCC sites must be entered into the WISER system. Once these AEs and SAEs are entered in WISER, certain actions must be taken regarding the reporting of specific Adverse Events to the DSMC.

All Adverse Events that occur during protocol intervention (defined below) and are coded as either 1)

unexpected grade 4, 2) unplanned inpatient hospitalization > 24 hours (regardless of grade), or grade 5 (death) must be reported to the DSMC using the SAE console in WISER.

A research nurse or clinical research coordinator when made aware that an adverse event meets one of the above criteria has occurred on a WFBCCC Investigator Initiated interventional trial, is responsible for informing a clinical member of the DSMC by phone (or in-person) about the adverse event. The nurse/coordinator should contact the treating physician prior to calling the DSMC clinical member to obtain all details of the SAE, as well as all associated toxicities to be recorded along with the SAE. In addition, this nurse or coordinator is responsible for entering the adverse event information into the SAE console in WISER. Once the adverse event has been entered into the SAE console an email informing the entire DSMC will be generated.

THESE REPORTING REQUIREMENTS APPLY TO any staff member on the study team for a WFBCCC Institutional Interventional trial. Ultimately, the protocol PI has the primary responsibility for AE identification, documentation, grading and assignment of attribution to the investigational agent/intervention. However, when an AE event as described above is observed, it is the responsibility of the person who observed the event to be sure that it is reported to the DSMC.

What is considered during protocol intervention?

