During protocol intervention is considered to be the time period while a patient is on study treatment or during the time period within 30 days of last study treatment (even if patient begins a new (non-study) treatment during the 30 days). This window of 30 days should be the standard window to be used in all protocols unless a specific scientific rationale is presented to suggest that a shorter window can be used to identify events. If it is a trial sponsored by Industry and the sponsor requires a longer window for monitoring of SAEs, then the longer window of time specified by the sponsor should be followed.

What is considered as an Unexpected Grade 4 event?

Any grade 4 event that was not specifically listed as an expected adverse event in the protocol should be considered as unexpected. A grade 4 adverse event can be considered to be unexpected if it is an event that would not be expected based on the treatment being received or if it is unexpected based on the health of the patient. In either case, if there is any uncertainty about whether a grade 4 adverse event is expected or unexpected it should be reported to DSMC.

DSMC notification responsibilities of the person (e.g., nurse) handling the reporting/documenting of the SAE in WISER:

1. Make a phone call (or speak in person) to the appropriate clinical member of the DSMC according to the schedule as listed below (page if necessary).
2. Enter a new SAE into the SAE module that is located in the Subject>> CRA Console inWISER WITHIN 24 HOURS of first knowledge of the event. Information can be entered and saved, but the DSMC members will not be notified until a date is entered into the DSMC Notification Date Field. This will ensure that all persons that need to be made aware of the event (i.e., PI, study team members and DSMC members) will be notified; remember to file a copy of the confirmation.
3. Document that the appropriate person(s) on the DSMC has been contacted. Indicate the name of the DSMC clinician that was contacted and the date and time contacted in the Event Narrative field in the SAE console of the particular subject.
4. Document whether or not the protocol should be suspended based on the discussion with the DSMC clinician. This is the major function of the email notification. Enter whether the protocol

should be suspended in the Event Narrative Field.

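### The 1-month AE log pre-prints Expected = 1 for ten acute toxicities whatever the treated area, which contradicts Section 8.1 and risks miscoding some grade 4 events

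*Combined protocol and SAP*

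**What the plan says.** Appendix I has two log pages. The 1-month page has eleven event rows and a column headed "Expected 1=Yes 0=No". A 1 is printed there for nausea, vomiting, diarrhea, skin erythema, alopecia, esophagitis, myelosuppression, urinary urgency, urinary frequency and pneumonitis. The eleventh row, beginning "Pain (increased from baseline", has no code. The page for 2, 3 and 6 months lists five late events and pre-fills none of them. Neither page has a field for the treated area or a note on how expectedness is to be coded.

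Section 8.1 gives the rule behind the column: "Expected side effects, depending on the area treated, include nausea, vomiting, diarrhea, skin erythema and alopecia in the irradiated area", followed by the remaining terms. Section 8.2 says that expectedness is used "see Section 7.1 above) for expedited reporting purposes only". Section 8.3 lists the events that go to the DSMC, starting with "unexpected grade 4, 2) unplanned inpatient hospitalization" and ending with death. Appendix D repeats these triggers and adds a default: "Any grade 4 event that was not specifically listed as an expected adverse event in the protocol should be considered as unexpected". It then allows a grade 4 event to be judged unexpected in light of the treatment given or the patient's health, and tells staff to report when in doubt.

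**The concern.** Expectedness has one stated use in this protocol, which is expedited reporting. Sections 8.1 and Appendix D treat it as something to be decided for the patient and the event. The log supplies the same answer for every patient before the event has happened.

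The eligible sites in Section 3.1.4 include tibia, fibula, radius with or without ulna, and the bones of the hands or feet. For a patient treated only at such a site, the log still classes pneumonitis and esophagitis as expected. Section 8.3 and Appendix D both phrase the first DSMC trigger in terms of how the event has been coded. A wrong code on a grade 4 event could therefore mean that nobody starts a report. At stake is prompt DSMC sight of a small number of severe events that do not fit the treatment given.

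**Working it through.** No sample size, power or error rate is involved. The check is a count and a comparison of texts.

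**1. Count of pre-filled cells.** On the 1-month page, 10 of 11 rows carry a 1 and 1 of 11 is blank. On the 2/3/6-month page, 0 of 5 rows are pre-filled. The table was read from PDF, but the printed 1 falls in the eighth of twelve columns in all ten rows, and the eighth column is the expectedness column.

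**2. Match with 8.1.** The ten pre-filled terms are exactly the ten terms in 8.1, so the form is evidently meant to apply that list.

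**3. What was lost in the transfer.**

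| Element | Section 8.1 | Appendix I, 1-month page |
|---|---|---|
| Terms | Ten | The same ten |
| Depends on treated area | Yes | No; the area is not recorded on the page |
| Erythema and alopecia confined to the irradiated area | Yes | No |
| Grade limit | None | None |

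The form departs from 8.1 on area only. The lack of a grade limit comes from 8.1 itself.

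**4. One event followed through.** Take grade 4 pneumonitis in a patient treated only at the tibia. I assume that a limb bone is not an area for which 8.1 means pneumonitis to be expected; 8.1 does not map terms to areas.

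- Log: expected, as printed.
- 8.1: not expected, because the area condition fails.
- Appendix D, default sentence: it does not catch the event, because pneumonitis is a listed term.
- Appendix D, treatment-received test: it does catch the event, provided someone applies it.
- Appendix D, rule for doubt: it catches the event if someone is in doubt.
- 8.3 and Appendix D triggers: if the code stays at 1, the event is reportable only through a route that ignores expectedness, namely "unplanned inpatient hospitalization > 24 hours (regardless of grade), or grade 5 (death) must be reported to the DSMC".

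The exposed group is therefore grade 4 events, among the ten terms, implausible for the treated area, with neither a qualifying admission nor death.

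**5. Timing.** Appendix D's reporting period runs to 30 days after the last study treatment. The 1-month visit falls 3 to 6 weeks after the final treatment (21 to 42 days). The first visit using the other page falls at 7 weeks at the earliest (7 × 7 = 49 days), after that period has closed. Of the two pages, the pre-coded one is the one that overlaps the DSMC period.

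**6. Route back to the rule.** Section 8.2 sends the reader to Section 7.1 for expectedness. Section 7.1 is Pain Response; the list is in 8.1. Someone checking the printed code against the protocol is sent to the wrong place.

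**The case against.** The strongest reply is that the log does not decide what reaches the DSMC. Appendix D does, and it tests each grade 4 event against the treatment received, with an instruction to report if unsure. Appendix I is held in Epic/REDCap. DSMC reports go through the WISER SAE console, which has its own yes/no field for unexpectedness for each event. All adverse events must also be entered in WISER. For a qualifying event, staff contact the treating physician and then speak to a DSMC clinician. The same log has empty columns for grade, attribution, physician initials and SAE status, and its footnote counts life-threatening events as serious whatever their expectedness. The expectedness column offers 0, and nothing forbids changing the printed 1.

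Most of this stands. A reader might infer that the printed code takes such events out of the unexpected grade 4 route altogether, or switches that trigger off. The documents do not support that: no text makes the log code decisive, and admission and death stay reportable regardless. Nor does the higher dose in the two-fraction arm add much weight, since the events in question are remote from the treated site.

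What the reply does not remove is the contradiction with 8.1. The safeguards also depend on someone raising the question. The rule for doubt needs doubt, which a printed answer discourages. The WISER field for unexpectedness belongs to the SAE form, so it helps only once an SAE entry has been opened. The log's own column on reportability names the IRB, STRC, FDA and sponsor, but not the DSMC.

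**Conclusion.** Wrong as written, minor. The 1-month log contradicts 8.1 by dropping the area condition for all ten terms, and it pre-empts the judgement in Appendix D. The consequence is a risk of misclassification for a narrow group of grade 4 events. It is not a disabled safety trigger.

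The count of 10 in 11 rows describes the form, not misrouted events. The documents give no rate for grade 4 toxicity remote from the treated area, so no number of patients can be put on it; it is probably small. The conclusion rests on two assumptions: that the printed 1s are in the expectedness column as the extracted table shows, and that some coordinators would take a printed code at face value.

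A reader might also infer that the form is at fault for covering grade 4, and want a grade ceiling on the code. That does not follow. Section 8.1 sets no ceiling either, and Appendix D's default treats listed events differently from unlisted ones on purpose. A ceiling below grade 4 would make every grade 4 event unexpected, which would rewrite the trigger in 8.3 and the institutional procedure in Appendix D.

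**What to change.** - In Appendix I, leave the ten expectedness cells on the 1-month page blank, as they already are on the 2/3/6-month page.
- Add one line to the form: expectedness is coded for each event against Section 8.1, the area treated in that patient, and the grade 4 guidance in Appendix D.
- In Section 8.2, change the cross-reference for expectedness from 7.1 to 8.1.

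No grade limit should be added. The cost is a form edit, one sentence and a corrected reference, with possibly a few more DSMC notifications. The trigger definitions in 8.3 and Appendix D need no change for this point.
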